3.7 Measurements of Dependent Variables

3.7.1 Anthropometrics, Blood Pressure, and Body Composition

Anthropometric and body composition measures took place at pre- and post-intervention points. Anthropometric measures of body mass (BM) (kg) and height (cm) were measured by a digital scale and stadiometer (SECA, Hamburg, Germany), respectively. Blood pressure was measured at baseline and the taper session of week 12 using an automated blood pressure machine (Omron, HEM-907XL, Vernon Hills, IL) after participants were seated, with their feet flat and arms rested at heart level for 5 minutes. Body composition was assessed via DXA (iDXA Lunar, GE, Madison, WI) by a trained technician. DXA is a commonly utilized, non-invasive assessment that uses x-ray to scan the body while in the supine position, which takes approximately 5-7 minutes. After completion of the body scan, the DXA system software determines the differences in attenuation of x-rays of two different energies among bone mineral content and soft tissue (lean and fat mass), from which body composition components fat mass, lean mass, and percent body fat can be calculated using machine specific algorithms (360). Unfortunately, due to a change in IRB regulations, after completing 8 DXA scans, we were no longer able to use that machine, and therefore, we measured body composition with a BIA machine (BIA 310e, Biodynamics Corp., Shoreline, WA). BIA is a commonly used, non-invasive method that uses a small test current (800 μ A at 50 kHz) to assess impedance, which is used to estimate body fat percentage. For the assessment, participants were asked to lie in a supine position, while two pairs of electrocardiography electrode tabs were placed on the right ankle and wrist. Thereafter, the test current was applied, and body composition was computed within the BIA machine. Test-rest reliability measured by intraclass correlation coefficients (model 3,1) for the body composition variables were: percent body fat, 0.969 (95% confidence

intervals: 0.753, 0.997); lean mass 0.994 (95% confidence intervals: 0.949, 0.999); fat mass 0.978 (95% confidence intervals: 0.826, 0.998).

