3.1 Overview of Experimental Design

The overarching aim of this project was to compare the traditional recommendation of immediate post-exercise protein consumption with nighttime pre-sleep protein intake during 12 weeks of resistance training on functional and cognitive adaptations in older adults. To achieve this, our design contained three groups who performed the same 12-week RET program two times per week and: 1) Consumed protein immediately post-exercise (Post-ex), 2) Consumed protein 30 minutes prior to sleep (Pre-sleep), or 3) Did not consume additional protein – exercise only (Ex only). Baseline total kilocalories (kcal) and protein intake were monitored to ensure no significant differences among groups occurred. The dependent variables consisted of pre- to post-intervention changes in body composition (i.e. lean mass, fat mass, and percent body fat), functional capacity (i.e. SPPB), nitrogen balance, free plasma insulin-like growth factor 1 (IGF-1), profile of mood states, and sleep evaluation, and digit symbol substitution and pattern comparison. Pre-, mid-, and post-intervention 1-RM, muscular power, and muscle thickness were assessed to determine the time course of muscular adaptations and appetite changes.

The pre-intervention measures took place over 2-3 days. All participants were instructed to refrain from vigorous physical activity at least 48 hours prior to all pre-testing measurements. On day 1, participants reported to the laboratory in the morning following an overnight fast (participants were encouraged to consume normal water intake) to complete the informed consent process, health history, and physical activity questionnaires. Thereafter, participants completed pre-training assessments including height and weight, baseline blood pressure, psychological and cognitive assessments, blood draw (IGF-1), body composition (DXA or BIA),

muscle thickness, muscular power, and the SPPB. Following the completion of day 1 assessments, participants were provided a 3-day food record, actigraphy watch, and 24-hour urine collection jug (nitrogen balance) to return prior to beginning the RET portion of the study.

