3.4 Resistance Exercise Training Protocol

All participants completed 12 weeks of RET, 2 times per week on non-consecutive days (separated by 72–96 hours). Participants generally completed their exercise at a consistent time (± 1 hour) throughout the study (e.g., every Monday at 1 pm). Research personnel and certified

personal trainers supervised all RET sessions, which took place in Strength Training Laboratory of the Sandels building. Each resistance exercise session began with 5 minutes of cycling at 50 revolutions per minute at 0.5 kg of resistance on a stationary cycle (Monark 828E, Langley, WA) followed by a standardized dynamic warm-up consisting of body weight movements to prepare the muscles for the specific exercises being performed. Thereafter, participants completed 3 lower body (leg press, leg extension, and leg curl) exercises and 5 upper body (chest press, shoulder press, latissimus row, triceps dip, and biceps curls) and for 3-4 sets and 4-12 repetitions with a 2-3-minute rest period between each set and exercise (see Table 1 for specific details). The chest press and leg press exercises were considered as the primary exercises, while all others were considered as accessory exercises. For the primary exercises, intensity was based upon 1-RM testing results. However, estimated 1-RM values were used for accessory exercises, which were established during week 1 of the RET protocol. Thereafter, a repetitions in reserve-based rating of perceived exertion (RIR-based RPE) scale was used to adjust load accordingly (149, 379). Exercise intensity was adjusted after the mid-testing 1-RM assessment to account for changes in maximum strength. However, for secondary exercises, intensity was adjusted each session based on participants RPE rating.

The 12-week RET program was designed as a periodized mesocycle, comprised of several specific microcycles (Table 1). Week 1 was an introductory microcycle of lower volume and intensity exercise (182). The aim of this week was to acclimate participants to exercise and elicit the repeated bout effect to attenuate muscle damage in the subsequent weeks of the program. On day 1 of the introductory week participants were assigned 2 sets of 12 repetitions at 50% 1-RM and 1 set of 10 repetitions at 55% 1-RM. Thereafter, weeks 2-6 consisted of two subsequent volume-focused microcycles. On day 1 of weeks 2-4, on day 1, participants were

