assigned 3 sets of 12 repetitions at 60% 1-RM and 3 sets of 10 repetitions at 65% 1-RM on day 2. On Day 1 of weeks 5-6, on day 1, participants were assigned 3 sets of 10 repetitions at 65% 1-RM and 3 sets of 8 repetitions at 70% 1-RM on day 2. Week 7 consisted of a taper on day 1, which was comprised of 2 sets of 2 repetitions at 80% 1-RM, followed by 1 set of 1 repetition at 85% 1-RM. On day 2 mid-intervention 1-RM assessments were completed for the chest press and leg press exercises followed by the normal exercise protocol for the accessory exercises. Then weeks 8-11 consisted of two subsequent intensity-focused microcycles, where intensity was based upon the mid-testing 1-RM value. For weeks 8-9, participants were assigned 3 sets of 8 repetitions at 70% 1-RM on day 1 and 3 sets of 6 repetitions at 75% 1-RM on day 2. For weeks 10-11, participants were assigned 3 sets of 6 repetitions at 75% 1-RM on day 1 and 4 sets of 4 repetitions at 80% 1-RM on day 2. Week 12 also consisted of a taper on day 1 and post-intervention 1-RM assessment on day 2. Only primary exercises were performed on taper days. Accessory exercises were completed with the same sets and repetitions as the main exercise; however, the load was selected to produce an RPE value between 6-8 and 7-9 for weeks 1-6 and 7-12, respectively. The intensity, sets, repetitions, number of exercises, and rest periods of the exercise program were in agreement with previous literature examining the effectiveness of RET on strength and LBM adaptations in older adults (270, 271).

Table 1. Overview of Exercise Training Program

Week	Focus	Day 1	Day 2
1	Introductory	2x12 @ 50%	2x10 @ 55%
2-3	Volume	3x12 @ 60%	3x10 @ 65%
4	Volume	[contact]%	[contact]%
5-6	Volume	3x10 @ 65%	3x8 @ 70%
7	Taper/Mid 1-RM test	2x2 @ 80%, 1x1 @ 85%	Mid 1-RM test
8-9	Intensity	3x8 @ 70%	3x6 @ 75%
10-11	Intensity	3x6 @ 75%	4x4 @ 80%
12	Taper/Post 1-RM test	2x2 @ 80%, 1x1 @ 85%	Post 1-RM test

RM = Repetition Maximum

If participants were not able complete the prescribed number of repetitions within a set, the training load for the subsequent sets of that specific exercise was reduced by approximately 2.5% for each missed repetition. For example, if a participant was only able to complete 4 of 6 assigned repetitions, then the load for the subsequent sets was reduced by 5%.

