3.5 Protein Supplementation

Protein and placebo supplementation were provided in a double-blind, placebo-controlled manner throughout the 12-week intervention. Participants were randomly assigned (<https://www.randomizer.org>) to 1 of 3 groups: 1) Post-ex consumed a protein supplement immediately post-exercise and a non-caloric placebo 30 minutes before sleep, 2) Pre-sleep consumed a non-caloric placebo immediately post-exercise and the protein supplement 30 minutes prior to sleep, or 3) Ex only did not consume protein or placebo supplementation. Participants were instructed to fast for at least 2 hours prior to each exercise session and for 2 hours post exercise (9), except for the consumption of the protein or placebo supplement, along with a 190-kcal snack bar (Nature Valley™, Oats 'N Honey, General Mills, MN), to reduce the timing effects of normal meals on exercise adaptations. Additional instructions were given to consume the nighttime pre-sleep protein or placebo supplement at least 2 hours after their last feeding (e.g. meal or snack) and approximately 30 minutes before sleep with no other food. On non-exercise days, participants were instructed to consume the protein or placebo supplement in between their normal breakfast and lunch.

To ensure a double-blind, placebo-controlled design, an assistant not associated with outcome measures created containers of protein and placebo supplements in advance and did not reveal the identity until the conclusion of the study. Participants were provided two containers with approximately 25 servings (3.5 weeks of supplements) of protein and placebo

supplementations. Each serving was weighed on a digital scale (Etekcity Co., Anaheim, CA) and placed within individual sealable bags (Ziploc; SC Johnson Co., Racine, WI) to ensure accurate servings. Furthermore, both supplements were masked for flavor, and texture. Lastly, participants were instructed to mix their supplement only with water.

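### Blood pressure is read fasted in the morning at baseline but at a training session in week 12, so its pre-to-post change cannot be cleanly read as a training effect

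*Combined protocol and SAP*

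**What the plan says.** **Baseline.** Section 3.1 describes the first visit: "On day 1, participants reported to the laboratory in the morning following an overnight fast". The assessments listed for that visit include "height and weight, baseline blood pressure, psychological and cognitive assessments".

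**Follow-up.** Section 3.7.1 ties the second reading to a training day: "Blood pressure was measured at baseline and the taper session of week 12". Section 3.4 confirms what that day is: "Week 12 also consisted of a taper on day 1 and post-intervention 1-RM assessment on day 2". Table 1 gives the taper as 2x2 at 80% and 1x1 at 85% of 1-RM.

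**Conditions of training sessions.** On timing, section 3.4 says: "Participants generally completed their exercise at a consistent time (± 1 hour) throughout the study (e.g., every Monday at 1 pm". On food, section 3.5 says: "Participants were instructed to fast for at least 2 hours prior to each exercise session".

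**What is held constant.** Section 3.7.1 names one automated device and one procedure for both readings, taken "after participants were seated, with their feet flat and arms rested at heart level for 5 minutes".

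**Analysis.** Section 3.8 applies a 3x2 (group by pre/post) mixed ANOVA to all dependent variables except four named ones that have three time points. Blood pressure is not one of the four. It is described under section 3.7, whose heading covers the dependent variables, but it is missing from the list of dependent variables in section 3.1 and from the lists for the three aims in section 3.2.

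**The concern.** A pre-to-post comparison is interpretable when the two readings are taken under like conditions, or when a control group shows what the change of conditions does on its own. Here the baseline conditions are fixed (morning, overnight fast, assessment visit), while the follow-up conditions are those of a training session. All three groups train, so no untrained group could separate the effect of 12 weeks of exercise from the effect of a different hour, a more recent meal or the exercise setting. The ANOVA in section 3.8 has no term for reading conditions.

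What is at stake is the time main effect on blood pressure. If it were significant, section 3.8 would follow it up with pairwise comparisons, and a change caused partly by reading conditions could be reported as an adaptation to training.

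**Working it through.** The plan states no blood pressure figure to reproduce: it gives no mean, SD or target difference. The check is therefore a comparison of the two readings, condition by condition.

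| Condition | Baseline reading | Week-12 reading | Matched by the text? |
|---|---|---|---|
| Device | Automated monitor (3.7.1) | Same | Yes |
| Posture and rest | Seated, 5 minutes (3.7.1) | Same | Yes |
| Time of day | Morning (3.1) | Participant's usual training hour; 1 pm is given as an example (3.4) | No |
| Food | Overnight fast (3.1) | Fast of at least 2 hours (3.5) | No |
| Setting | Assessment visit (3.1) | Loaded training session (3.4, Table 1) | No |
| Order relative to exercise | Among the day-1 assessments (3.1) | Not stated | Unknown |
| Recent vigorous exercise | None for at least 48 hours (3.1) | Sessions 72–96 hours apart (3.4) | Carry-over from the previous session unlikely |

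**Which comparison is affected.** Write the observed mean change in group g as T_g + C_g, where T_g is the true change and C_g the shift due to reading conditions.

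- The time effect averages T_g + C_g over the groups, so it contains the average of C_g in full.
- The group x time contrast is (T_1 − T_2) + (C_1 − C_2). The schedule is the same for all groups and assignment is random, so C_1 − C_2 is expected to be about zero. Differences in training hour between men add noise rather than systematic bias.

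**Whether the size can be calculated.** It cannot be calculated from the documents. The following illustration assumes that the change of conditions shifts every man's reading by a common amount, that the SD of change is 10 mmHg, and that training has no effect. With 30 men in 3 groups, error df = 30 − 3 = 27, and the noncentrality parameter is shift / (SD / √30). The two-sided 0.05 critical value is 2.052.

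| Assumed shift (mmHg) | Noncentrality | Chance of a significant time effect |
|---|---|---|
| 1 | 1 / (10/√30) = 0.55 | 8% |
| 2 | 1.10 | 18% |
| 3 | 1.64 | 35% |
| 5 | 2.74 | 75% |
| 8 | 4.38 | 99% |

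For a 5 mmHg shift, an assumed SD of 8 gives 91% and an SD of 12 gives 60%. The result runs from close to the nominal 5% to near certainty, depending only on an assumed shift. The table shows how strongly the answer depends on that input. It is not an estimate of the bias in this trial.

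**The case against.** The strongest reply is that blood pressure may not be an outcome at all. Section 3.1 says what the dependent variables were and does not include it; nor do the lists in section 3.2. Height is described in the same subsection and is plainly not an outcome. No hypothesis or correlation concerns blood pressure. This largely stands and is the main reason the point is minor. It does not dispose of the point: a repeat reading at week 12 invites a comparison, and the heading of section 3.7 together with the wording of section 3.8 would bring blood pressure into the ANOVA.

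A second reply is that section 3.1 says post-intervention measures were taken in a similar way to the baseline ones. That is a general sentence, and section 3.7.1 is specific about the occasion. For appetite (3.7.5.1) and IGF-1 (3.7.7) the plan states the overnight fast at both time points; for blood pressure it does not. If the taper session also served as a fasted morning visit, one sentence would settle the matter.

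A third reply is that without an untrained group no time effect in this trial can be attributed cleanly to training. That is true, but a change in reading conditions is an additional and avoidable source of bias.

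Three stronger readings are tempting and are not supported:

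- A reader might infer that conditions differed for every man. The 1 pm slot is only an example and 2 hours is a minimum, so someone who trained in the morning could match baseline on time and possibly on fasting. Conditions are uncontrolled, not shown to differ throughout.
- A reader might infer that the second reading followed the lifts. No section says so.
- A reader might infer that the comparison of protein timing is compromised. The shared schedule largely protects it.

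**Conclusion.** The point holds as a minor one. The text sets different occasions for the two readings and leaves time of day, fed state and setting uncontrolled between them, so a pre-to-post time effect on blood pressure should not be presented as a training effect. The group x time comparison is largely protected, and the three specific aims do not depend on blood pressure.

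The conclusion rests on reading section 3.7.1 as the governing statement for the second reading, and on the taper being run under the general session rules of sections 3.4 and 3.5. No numerical size can be given: neither the shift due to conditions nor the SD of change is in the documents, and the direction of any shift is also unknown.

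**What to change.** **For the protocol, or any repeat of it.** In section 3.7.1, replace the taper session with the fasted morning post-test visit already used for the IGF-1 blood draw (section 3.7.7). State that the reading is taken before any exercise and at the same stage of the visit as on day 1. This moves a reading with a 5-minute seated rest to a visit that already takes place, so the cost is close to nil.

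**If the data are already collected**, as the past tense and the final group sizes in section 3.3 suggest:

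- State in section 3.8 that blood pressure is excluded from the pre/post ANOVA and reported descriptively only.
- State the difference in reading conditions next to the results.
- Give clock time, fed state and order relative to exercise where these were recorded. The documents do not say that they were; if not, say so.

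This costs a few sentences and gives up no comparison on which the aims rely.

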3.8 Sample Size Justification and Statistical Analysis

An a priori analysis was conducted with an effect size F of 0.25 calculated using mean and standard deviations from previously reported changes in LBM in older men (350) with power set to 0.8 and α set to 0.05 for 3 groups and 3 measurements. With an expected dropout rate of 15% (110), a sample size of 36 was adequate and provided an even distribution between groups.

A one-way analysis of variance (ANOVA) was used to analyze baseline differences and total training volume among groups. A 3x2 mixed model ANOVA with group as the between subjects' factor (Post-ex, Pre-sleep, Ex only) and time as the within-subjects factor (pre and post) was performed on all dependent variables except for muscle thickness, 1-RM strength, muscle power, and appetite, where a 3x3 mixed model ANOVA (Post-ex, Pre-sleep, Ex only x pre, mid, post) was used. Pearson product-moment correlation, or Spearman's correlation in the event of normality violation, was used to determine the relationship between changes in free IGF-1 and changes in body composition, muscle thickness, 1-RM strength, muscular power, and cognitive assessments.

Outliers were removed and defined as values outside of the mean \pm 3 standard deviations. Data were tested for normality (Shapiro-Wilk), homogeneity of variances (Levene's test), and sphericity (Mauchly's test) where appropriate. When normality or homogeneity of variances was violated, non-parametric testing or data transformation was performed. For a mixed model ANOVA, if transformation could not correct the violation, original data were analyzed, as there are no non-parametric alternatives. When sphericity was violated, the main time and group x time interactions were interpreted with the Greenhouse-Geisser estimation.

Significance was set at $p \leq 0.05$. Trends were noted for p -values between 0.051-0.10. For significant interactions and main effects, pairwise comparisons with Bonferroni adjustments were conducted (296, 332). Pearson correlation coefficients (r) or Spearman's correlation coefficients (r_s) were interpreted as "negligible" = < 0.30 , "low" = $0.30-0.50$, "moderate" = $0.50-0.70$, "high" = $0.70-0.90$, and "very high" = > 0.90 (244). Percentage change was calculated as $((\text{post value} - \text{pre value}) * 100)$. All analyses were performed with SPSS version 25

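### Body composition moved from DXA to BIA after 8 scans, but the analysis has no device term or same-device rule, so the device offset counts as change for any man who switched (0 to 8 of 30)

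*Combined protocol and SAP*

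**What the plan says.** Section 3.7.1 has two body-composition visits: "Anthropometric and body composition measures took place at pre- and post-intervention points". It then states that "after completing 8 DXA scans, we were no longer able to use that machine, and therefore, we measured body composition with a BIA machine". The design overview in section 3.1 lists "body composition (DXA or BIA" among the baseline tests, without saying which man gets which device.

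Section 3.8 puts body composition in the general model. The 3x2 mixed ANOVA (three groups, pre and post) "was performed on all dependent variables except for muscle thickness, 1-RM strength, muscle power, and appetite", so lean mass, fat mass and percent fat are analysed with group and time as the only factors. The same section also correlates the "relationship between changes in free IGF-1 and changes in body composition". The effect size behind the sample size comes from "previously reported changes in LBM in older men".

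Nowhere do the documents give a rule that both visits use one device, a DXA-BIA calibration, a repeat baseline on BIA, an exclusion of mixed pairs, or the number of men on each device by arm and visit.

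**The concern.** A pre-post comparison assumes that both visits measure the same quantity on the same scale. If a man is measured by DXA at baseline and by BIA after training, any systematic difference between the devices enters his change score, and the planned model cannot separate it from a training effect. Men measured twice on one device are not affected by a constant offset.

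Three analyses could suffer:

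- the time effect (did lean or fat mass change over training), through bias;
- the group-by-time test, through added variance and, if switched men are unevenly spread over the arms, through bias in the timing contrast;
- the correlations of IGF-1 change with body-composition change, through the same error.

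Body composition is the first outcome listed under Specific Aim 1. Muscle thickness, strength, power and SPPB are untouched.

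**Working it through.** **Inputs from the documents.** 8 DXA scans and 2 visits per man (section 3.7.1); 30 men in arms of 9, 11 and 10 (section 3.3); a model with group and time only (section 3.8). The plan gives no figure for DXA-BIA agreement, so there is none to reproduce. The planned sample size of 36 does not enter the argument.

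**Assumed inputs, not in the documents.** SD of true change 1.5 kg; true effect 2 kg in both protein arms and 0 in Ex only; mean device offset 0 to 4 kg; person-level SD of the device difference 1.5 kg (0.5 and 2.5 kg as sensitivity).

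**Step 1: how many could have switched.** If *a* men had DXA at both visits and *b* at baseline only, then 2*a* + *b* = 8. Four complete pairs give *b* = 0, two pairs plus four baselines give *b* = 4, and eight baselines give *b* = 8. If DXA men were measured again on BIA before training, or if some scanned men are not among the 30, the number is lower. The range is 0 to 8.

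**Step 2: bias in the time effect.** For a switched man, observed change = true change + offset + a personal deviation. Mean bias = offset × *s*/30, where *s* is the number switched: 0 for none, 4/30 = 0.13 and 8/30 = 0.27 kg per kg of offset.

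**Step 3: power and error rates.** Simulation with 8,000 to 20,000 runs per scenario, switched men chosen at random. Group-by-time is the one-way F test on change (2 and 27 df; 2 and 26 with a switch term). The time effect is a t test on the mean of the three arm means.

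| Quantity | Offset | 4 switched | 8 switched |
|---|---|---|---|
| Group-by-time power, plan's model | 0 kg | 0.791 | 0.741 |
| | 2 kg | 0.715 | 0.625 |
| | 4 kg | 0.544 | 0.415 |
| Power with switch term | 0 / 2 / 4 kg | 0.786 / 0.781 / 0.778 | 0.728 / 0.730 / 0.729 |
| Power, same-device men only | any | about 0.77 | about 0.67 |
| Time-effect false positives, plan's model | 1 / 2 / 4 kg | 0.07 / 0.10 / 0.20 | 0.11 / 0.28 / 0.69 |

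With nobody switched, power is 0.835. At a 2 kg offset, device SDs of 0.5 and 2.5 kg give 0.75 and 0.65 (4 switched) or 0.69 and 0.52 (8 switched). With no true change, the group-by-time rejection rate stays at 0.045 to 0.052. The time-effect rate at 2 kg returns to 0.03-0.04 with the switch term and 0.048 in same-device men.

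**Step 4: the timing contrast.** Bias in Pre-sleep minus Post-ex = offset × difference in switched shares. Under random spread it is centred on zero, with variance *p*(1 − *p*) × (30/29) × (1/9 + 1/11), where *p* = *s*/30. The SD is 0.155 (4 switched) or 0.202 (8 switched) per kg of offset. The extreme case, all eight in Post-ex, is 8/9 = 0.89 kg per kg.

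**Step 5: the IGF-1 correlations.** Variance of observed change = 2.25 + *p* × 2.25 + *p*(1 − *p*) × offset². At 2 kg:

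- 4 switched: 2.25 + 0.30 + 0.46 = 3.01; factor √(2.25/3.01) = 0.864; a correlation of 0.60 becomes 0.52.
- 8 switched: 2.25 + 0.60 + 0.78 = 3.63; factor √(2.25/3.63) = 0.787; 0.60 becomes 0.47, which drops from the plan's moderate band to its low band.

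**Step 6: do existing safeguards catch it?** The ICCs in section 3.7.1 name no device and describe test-retest repeatability, not agreement between devices. Under the 3 SD outlier rule, the offset alone places switched men at most √((30 − *s*)/*s*) SD from the mean change: 2.5 for 4 switched and 1.7 for 8. Section 3.1 says post-testing followed the baseline procedure, but that is not a same-device rule. A man scanned on DXA at baseline could not meet it on DXA once the machine was lost.

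**The case against.** The strongest reply is that the harm is conditional. No sentence says that any man was measured on different devices at the two visits, and zero switched is within the range. This stands: what the text establishes is the change of device and the absence of any handling of it. Four complete pairs, however, would require that only four men had been scanned when those four finished 12 weeks of training.

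Second, Aim 1 concerns protein timing, which is the group-by-time test. Assignment was random, so that test keeps its size and there is no documentary reason to expect imbalance. This is right, and the high false-positive rates belong to the time effect only. But section 3.8 also tests and follows up main effects, and the power loss falls on the group-by-time test itself.

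Third, the magnitudes are illustrative. The 0.84 starting power follows from the assumed effect (about f = 0.63 on change scores), which equals the plan's f = 0.25 only at a pre-post correlation near 0.7. The two protein arms are given the same effect, so the losses do not describe power for the timing contrast. The sample size calculation also uses three measurements, whereas body composition has two. All of this is fair, and the figures should be read as a range.

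Fourth, a switch term would rest on at most 8 men. True, and this is why the same-device analysis belongs beside it.

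**Conclusion.** The concern holds. Followed as written, the plan counts the device offset as change for every man who switched, and nothing else in the documents corrects this. Confidence is high for the omission; whether bias actually occurred depends on a count that is not reported.

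If nobody switched, the change analyses stand. Up to four DXA pairs beside BIA pairs would still mix devices in the baseline comparison and the group main effect.

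If men did switch, the main consequences are a biased time effect and lost group-by-time power. The sizes shown depend on the assumed offset, SDs and true effect. The timing contrast is biased only so far as switched men are unevenly spread over the arms, which cannot be judged without the counts. This should be fixed, since it can be done with data already held.

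**What to change.** 1. Report the number of men on each device by arm and visit, and say whether any DXA man had a repeat baseline on BIA.
2. If nobody switched, keep the model and note any mixing of devices at baseline.
3. If any man switched, add a switched-by-time term (a switched indicator in the model for change) for lean mass, fat mass and percent fat, and estimate the time effect from same-device pairs.
4. Show the same-device-only analysis as a sensitivity check.
5. For the IGF-1 correlations with body-composition change, use a partial correlation on the switched indicator, or same-device pairs only where Spearman is used.

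The cost is a table, some analysis wording and a rerun. The term uses one degree of freedom and about 0.01 of power if the offset is really zero (0.791 to 0.786, or 0.741 to 0.728). With 8 switched at 2 kg it recovers about 0.10 (0.625 to 0.730).

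Exclusion alone is usually dearer here, but with a device SD of 2.5 kg and 8 switched the order reverses (0.59 with the term, 0.67 with exclusion), so both should be shown. Exclusion leaves 22 to 30 men. At the plan's f = 0.25, group-by-time power at 30 and 22 men is 0.64 and 0.48 for an assumed pre-post correlation of 0.5, and 0.86 and 0.71 for 0.7.
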